### 5.2.1 Adverse Events

According to the ICH guideline for GCP, an adverse event is any untoward medical occurrence in a clinical investigation subject administered a pharmaceutical product, regardless of causal attribution. An adverse event can therefore be any of the following:

- Any unfavorable and unintended sign (including an abnormal laboratory finding), symptom, or disease temporally associated with the use of a medicinal product, whether or not considered related to the medicinal product
- Any new disease or exacerbation of an existing disease (a worsening in the character, frequency, or severity of a known condition), except as described in Section 5.3.5.10
- Recurrence of an intermittent medical condition (e.g., headache) not present at baseline

- Any deterioration in a laboratory value or other clinical test (e.g., ECG, X-ray) that is associated with symptoms or leads to a change in study treatment or concomitant treatment or discontinuation from study drug
- Adverse events that are related to a protocol-mandated intervention, including those that occur prior to assignment of study treatment (e.g., screening invasive procedures such as biopsies)

### **5.2.2 Serious Adverse Events (Immediately Reportable to the Sponsor)**

A serious adverse event is any adverse event that meets any of the following criteria:

- Is fatal (i.e., the adverse event actually causes or leads to death)
- Is life threatening (i.e., the adverse event, in the view of the investigator, places the patient at immediate risk of death)

This does not include any adverse event that had it occurred in a more severe form or was allowed to continue might have caused death.

- Requires or prolongs inpatient hospitalization (see Section 5.3.5.11)
- Results in persistent or significant disability/incapacity (i.e., the adverse event results in substantial disruption of the patient's ability to conduct normal life functions)
- Is a congenital anomaly/birth defect in a neonate/infant born to a mother exposed to study drug
- Is a significant medical event in the investigator's judgment (e.g., may jeopardize the patient or may require medical/surgical intervention to prevent one of the outcomes listed above)

The terms "severe" and "serious" are not synonymous. Severity refers to the intensity of an adverse event (e.g., rated as mild, moderate, or severe, or according to NCI CTCAE; see Section 5.3.3); the event itself may be of relatively minor medical significance (such as severe headache without any further findings).

Severity and seriousness need to be independently assessed for each adverse event recorded on the eCRF.

Serious adverse events are required to be reported by the investigator to the Sponsor immediately (i.e., no more than 24 hours after learning of the event; see Section 5.4.2 for reporting instructions).

### **5.2.3 Adverse Events of Special Interest (Immediately Reportable to the Sponsor)**

Adverse events of special interest are required to be reported by the investigator to the Sponsor immediately (i.e., no more than 24 hours after learning of the event; see Section 5.4.2 for reporting instructions). Adverse events of special interest for this study include the following:

- Cases of potential drug-induced liver injury that include an elevated ALT or AST in combination with either an elevated bilirubin or clinical jaundice, as defined by Hy's Law (see Section 5.3.5.7)
- Suspected transmission of an infectious agent by study treatment, as defined below  
Any organism, virus, or infectious particle (e.g., prion protein transmitting transmissible spongiform encephalopathy), pathogenic or non-pathogenic, is considered an infectious agent. A transmission of an infectious agent may be suspected from clinical symptoms or laboratory findings that indicate an infection in a patient exposed to a medicinal product. This term applies only when a contamination of any of the study treatment components is suspected.
- TLS of any grade, irrespective of causality
- Grade • 3 neutropenia, including febrile neutropenia
- Grade • 2 diarrhea
- Grade • 3 thrombocytopenia or Grade 2 thrombocytopenia if associated with hemorrhage/bleeding
- *Grade • 2 Clostridium difficile infection*
- *Second malignancies*

### **5.2.4 Dose-Limiting Toxicities (Immediately Reportable to the Sponsor)**

During the DLT assessment window, adverse events defined as DLTs (as defined in Section 3.1.2.1), are required to be reported by the investigator to the Sponsor immediately (no more than 24 hours after learning of the event; see Section 5.4.2).

### **5.2.5 Selected Adverse Events**

Selected adverse events in this study are defined as adverse events for which additional data collection or analyses will be performed. Selected adverse events do not require immediate reporting if they are not serious (except for TLS).

The following adverse events are considered selected adverse events:

- Thrombocytopenia, including acute thrombocytopenia (events occurring during and within 24 hours following obinutuzumab infusion)
- Hepatitis B reactivation
- Cardiac events

- TLS
- IRRs
- All infections, including PML
- Neutropenia, including prolonged neutropenia (neutropenia < 1000 cells/• L that does not resolve after 28 days without obinutuzumab treatment) and late-onset neutropenia (neutropenia < 1000 cells/• L occurring • 28 days after obinutuzumab treatment has been completed or stopped)
- Gastrointestinal perforation

Events for which additional data collection will be required are PML and hepatitis B reactivation.

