## 3. STUDY DESIGN

### 3.1 DESCRIPTION OF STUDY

#### 3.1.1 Overview of Study

This Phase Ib/II, open-label, multicenter, non-randomized, dose-escalation study will evaluate the safety, efficacy, and pharmacokinetics of idasanutlin in combination with obinutuzumab in patients with R/R FL *and rituximab in combination with idasanutlin in R/R DLBCL*. The study will include an initial dose-escalation phase *followed by an expansion phase*. *The dose-escalation phase is designed to determine the RP2D for idasanutlin in combination with obinutuzumab for FL and in combination with rituximab for DLBCL. Dose escalation starts with idasanutlin in combination with obinutuzumab in all patients (FL and DLBCL) until the MTD (Regimen A) (see Section 3.1.2) followed by:*

- *Dose confirmation and potential dose escalation in DLBCL patients for idasanutlin in combination with rituximab to determine the RP2D for this combination.*
- *Dose confirmation and potential dose escalation in FL patients for a different regimen (Regimen B, obinutuzumab given alone in Cycle 1 followed by*

*idasanutlin and obinutuzumab in combination from Cycles 2 to 6) to determine the RP2D for this regimen.*

*RP2D(s) and regimens for FL and DLBCL will be decided at the end of dose-escalation phase, and two different RP2Ds and/or regimens may apply for FL and DLBCL, respectively.*

*In the expansion phase, patients with FL will receive idasanutlin at the RP2D of the selected regimen (A or B) in combination with obinutuzumab, and patients with DLBCL will receive idasanutlin at the RP2D in combination with rituximab.*

[figure not shown]
*Patients with R/R FL enrolled in the dose-escalation phase may be eligible to receive post-induction treatment (referred to as maintenance) with obinutuzumab (see Section 3.1.2.2 and Section 3.1.3 for details on treatment regimens).*

*Patients with R/R FL enrolled in the expansion phase may be eligible to receive maintenance treatment with obinutuzumab and idasanutlin (see Sections 3.1.2.2 and 3.1.3, respectively, for details on the treatment regimens).*

*Patients with R/R DLBCL enrolled in the expansion phase may be eligible to receive post-induction treatment (referred to as consolidation) with rituximab and idasanutlin (see Section 3.1.3 for details on treatment regimens).*

A study schema is provided in [Figure 6](#). Refer to Sections [3.1.2](#) and [3.1.3](#) for details on the treatment regimens.

Figure 6 Study Schema

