### **5.1.1.3 Neutropenia**

Grade 3 or 4 neutropenia, including febrile neutropenia, has been reported with obinutuzumab administration. Neutropenia resolved spontaneously or with use of hematopoietic growth factors. Patients who experience Grade 3 or 4 neutropenia should be closely monitored until neutrophil values return to at least Grade 2. Cases of late-onset neutropenia (ANC < 1000 cells/ $\cdot$ L occurring  $\cdot$  28 days after obinutuzumab treatment has been completed or stopped) or prolonged neutropenia (ANC < 1000 cells/ $\cdot$ L that does not resolve after 28 days without obinutuzumab treatment) have also been reported. Prophylactic treatment with antibiotics should be administered as per standard practice. The use of G-CSF is allowed for treatment of neutropenia in this study. Guidelines for primary prophylaxis with G-CSF are provided in Section 4.4.1.

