### **5.1.1.4 Thrombocytopenia**

Severe and life-threatening thrombocytopenia, including acute thrombocytopenia (occurring within 24 hours after the infusion), has been observed during treatment with obinutuzumab. In patients with CLL exposed to obinutuzumab, fatal hemorrhagic events have also been reported in Cycle 1. A clear relationship between thrombocytopenia and hemorrhagic events has not been established. Patients should be closely monitored for thrombocytopenia, especially during the first cycle of treatment. For patients who experience thrombocytopenia, regular laboratory tests should be performed until the event resolves, and dose delays should be considered in case of severe or life-threatening thrombocytopenia. Transfusion of blood products (i.e., platelet transfusion) may be performed at the discretion of the treating physician, according to institutional practice.

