#### **5.1.2.5 Neutropenia (Including Prolonged Neutropenia)**

Neutropenia is very common in patients receiving rituximab (occurring in • 10% of patients) based on clinical trial experience. However, delayed onset neutropenia is very rare (occurring in < 1 of 10,000 patients), and the incidence of prolonged neutropenia is unknown. Neutropenia may lead to serious or overwhelming infection, especially if profound (Grades 3•4), prolonged, associated with breaches in natural mucosal barriers

(e.g., diarrhea and/or mucositis), and/or other immunological defects (e.g., lymphopenia, hypogammaglobulinemia, and acquired immunodeficiency syndrome). Despite an increase in incidence of neutropenia and Grade 3•4 neutropenia associated with rituximab, most studies have not reported a significant increase in serious neutropenic infections.

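### Section 5.2.5 times prolonged neutropenia, late-onset neutropenia and acute thrombocytopenia by obinutuzumab alone, so these subtypes cannot be properly classified in DLBCL patients who receive only rituximab

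*Combined protocol and SAP*

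**What the plan says.** Section 5.2.5 sets up a study-wide category: "Selected adverse events in this study are defined as adverse events for which additional data collection or analyses will be performed". Two of its entries contain subtypes with a time anchor:

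- Acute thrombocytopenia: "events occurring during and within 24 hours following obinutuzumab infusion".
- Prolonged neutropenia, a count below 1000 cells per microlitre "that does not resolve after 28 days without obinutuzumab treatment) and late-onset neutropenia". Late-onset neutropenia uses the same count, with onset judged against "28 days after obinutuzumab treatment has been completed or stopped".

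The same timings appear in only two other places, both in the obinutuzumab risk section. Section 5.1.1.3 says cases of prolonged neutropenia "that does not resolve after 28 days without obinutuzumab treatment) have also been reported". Section 5.1.1.4 describes severe thrombocytopenia, "including acute thrombocytopenia (occurring within 24 hours after the infusion), has been observed during treatment with obinutuzumab".

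On treatment, Section 3.1.1 states that in the expansion phase "patients with DLBCL will receive idasanutlin at the RP2D in combination with rituximab". Table 2 gives the DLBCL bridging cohort(s) rituximab, and Tables 6 and 7 do the same for expansion induction and consolidation. Section 5.1.2 lists prolonged neutropenia among the important rituximab risks. Section 5.1.2.5 adds that delayed-onset neutropenia is very rare, at under 1 in 10,000 patients, "and the incidence of prolonged neutropenia is unknown".

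**The concern.** Version 4 moved later DLBCL patients from obinutuzumab to rituximab, but these three definitions still name only obinutuzumab. A patient who never receives obinutuzumab has no obinutuzumab infusion and no date on which obinutuzumab ended, so the definitions have nothing to attach to.

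Section 2.1 makes the timing of adverse events part of the safety objective for both combinations, and Section 6 summarises expansion data by histology. A subtype table by histology would set real FL counts beside DLBCL entries that are zero or undefined because of wording. A reader could take that contrast for a difference between the two combinations.

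**Working it through.** The plan states no figure for this point and no formula applies. The check sets the definitions beside the treatment each group receives.

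**1. Who receives which antibody.** FL patients, and DLBCL patients in Regimen A escalation, receive obinutuzumab (Tables 2 and 6). DLBCL bridging and expansion patients receive rituximab (Tables 2, 6 and 7). Section 3.1.3 plans about 40 FL and 40 DLBCL expansion patients, so 40/80 = 50% of the expansion phase is on rituximab, plus the DLBCL bridging patients.

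**2. Applying each definition as written.**

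| Subtype | Anchor in 5.2.5 | Patient on obinutuzumab | Patient on rituximab only |
|---|---|---|---|
| Acute thrombocytopenia | Within 24 hours of an obinutuzumab infusion | Classifiable | No such infusion; count is 0 whatever happens |
| Late-onset neutropenia | 28-day threshold from the end of obinutuzumab | Classifiable | No such end date; count is 0 whatever happens |
| Prolonged neutropenia | Unresolved after 28 days off obinutuzumab | Clock starts at the last obinutuzumab dose | Never on obinutuzumab, so no clock start; undefined |

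**3. Is there a rituximab definition elsewhere?** No. Section 5.1.2.5 mentions delayed-onset and prolonged neutropenia under rituximab but gives neither a threshold nor a time anchor.

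**4. Is the restriction stated as intended?** Where Version 4 limits a rule to obinutuzumab recipients it says so, as for the two-year infection reporting and the second-malignancy reporting in Sections 5.3.1 and 5.6. Section 5.2.5 carries no such limit. Section 5.3.5.1 defines infusion-related reactions by study treatment infusion, so an antibody-neutral anchor is already used in this protocol.

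**5. Would the data allow classification?** Yes. Rituximab is given on Day 1 of each induction cycle. Appendix 2 places the end-of-induction visit 6 to 8 weeks after Day 1 of the last cycle, which is 6 × 7 = 42 to 8 × 7 = 56 days after that infusion. The end-of-consolidation visit is 35 days after the last dose. Both lie beyond 28 days. Section 5.3.1 collects all adverse events to 90 days after the last study treatment.

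**6. Would a common anchor mean the same thing in both groups?** Largely. From Cycle 2 both antibodies are given on Day 1 of a 28-day cycle, and both are given every 2 months after induction. The exception is Cycle 1, where obinutuzumab is also given on Days 8 and 15.

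**The case against.** The strongest reply is that little is lost. Section 5.2.5 lists thrombocytopenia and neutropenia as parent terms for every patient. Section 5.2.3 makes Grade 3 or higher neutropenia and thrombocytopenia, and Grade 2 thrombocytopenia with bleeding, adverse events of special interest whatever the antibody. Section 6.3 summarises and lists those events and displays laboratory values by time. It names no table of the three subtypes. Section 5.2.5 also confines required extra data collection to PML and hepatitis B reactivation, so only analysis is affected. All of this stands. A reader might infer that the DLBCL cohort would look falsely safe for cytopenias as a whole; the documents do not support that.

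Second, a reader might attach a rate to the missed late-onset cases. The documents give no rate for the combination. The only figure, for rituximab, is under 1 in 10,000, so the expected count in 40 patients is below 40 × 1/10,000 = 0.004. Idasanutlin may raise this (Table 15 shows 27% Grade 3 or higher neutropenia for it as a single agent), but by how much is not stated. No count of missed cases can be defended.

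Third, a reader might say prolonged neutropenia is over-counted in DLBCL, because a rituximab patient is always off obinutuzumab. That is one strained reading. It is equally open to say the 28 days never start, so the direction of error is indeterminate.

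Fourth, some of the anchoring may be deliberate. Section 5.1.1.4 describes acute thrombocytopenia only for obinutuzumab, and the important rituximab risks in Section 5.1.2 include prolonged neutropenia but neither of the other two subtypes. Version 4 also edited the selected-event list by moving second malignancies out of it. This has force for acute thrombocytopenia and some for late-onset neutropenia. It has none for prolonged neutropenia, which the amended protocol names as a rituximab risk of unknown incidence.

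**Conclusion.** The point holds as a defect in definition, limited to three subtypes. For rituximab-only DLBCL patients, late-onset neutropenia and acute thrombocytopenia are structural zeros and prolonged neutropenia is undefined. The definitions therefore fail for about 40 of 80 expansion patients and the DLBCL bridging cohort(s), but an error arises only when one of those patients has such an event. DLBCL patients given obinutuzumab in Regimen A are classified correctly. The case is firmest for prolonged neutropenia and weakest for acute thrombocytopenia.

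The consequence is confined to subtype classification and any FL versus DLBCL description built on it. Capture of the events, the primary endpoint, the DLT rules and the sample size are untouched.

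The conclusion assumes the definitions are applied literally, and that treatment follows Section 3.1.1 and Tables 2, 6 and 7. The synopsis paragraph on the investigational products mentions obinutuzumab during consolidation for eligible DLBCL patients. That disagrees with Section 3.1.1 and Table 7, and the passages must be reconciled.

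**What to change.** In Section 5.2.5, define prolonged and late-onset neutropenia relative to the anti-CD20 antibody the patient received (obinutuzumab or rituximab), and tabulate both by antibody. Tabulating by antibody rather than by histology keeps Regimen A DLBCL patients with the drug they were given.

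For acute thrombocytopenia, choose one of two courses. Either anchor it in the same way, or state that the subtype applies to obinutuzumab recipients only and show it as not applicable, rather than zero, for rituximab patients.

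The cost is a wording change in one section and matching table programs. It needs no new visits, samples or patients, and it changes no treatment or stopping rule.

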### **5.3 METHODS AND TIMING FOR CAPTURING AND ASSESSING SAFETY PARAMETERS**

The investigator is responsible for ensuring that all adverse events (see Section 5.2.1 for definition) are recorded on the Adverse Event eCRF and reported to the Sponsor in accordance with instructions provided in this section and in Sections 5.4•5.6.

For each adverse event recorded on the Adverse Event eCRF, the investigator will make an assessment of seriousness (see Section 5.2.2 for seriousness criteria), severity (see Section 5.3.3), and causality (see Section 5.3.4).

#### **5.3.1 Adverse Event Reporting Period**

Investigators will seek information on adverse events at each patient contact. All adverse events, whether reported by the patient or noted by study personnel, will be recorded in the patient's medical record and on the Adverse Event eCRF.

**After informed consent** has been obtained **but prior to initiation of study treatment**, only serious adverse events caused by a protocol-mandated intervention (e.g., invasive procedures such as biopsies, discontinuation of medications) should be reported (see Section 5.4.2 for instructions for reporting serious adverse events).

**After initiation of study treatment**, all adverse events will be reported until 90 days after the last study treatment. After this period, the investigator should report any serious adverse events that are believed to be related to prior study drug treatment.

An exception is made for Grade 3 or 4 infections (related and unrelated) *in patients who received obinutuzumab*, which should be reported up to 2 years after the last dose of *obinutuzumab*.

*Second malignancies will be recorded indefinitely for patients who received obinutuzumab (even if the study has been closed) (see Section 5.6).*

### 5.3.2 Eliciting Adverse Event Information

A consistent methodology of non-directive questioning should be adopted for eliciting adverse event information at all patient evaluation timepoints. Examples of non-directive questions include the following:

“How have you felt since your last clinic visit?”

“Have you had any new or changed health problems since you were last here?”

### 5.3.3 Assessment of Severity of Adverse Events

The adverse event severity grading scale for the NCI CTCAE, v4.0 will be used for assessing adverse event severity. Table 21 will be used for assessing severity for adverse events that are not specifically listed in the NCI CTCAE.

**Table 21 Adverse Event Severity Grading Scale for Events Not Specifically Listed in NCI CTCAE**

Grade	Severity
1	Mild; asymptomatic or mild symptoms; clinical or diagnostic observations only; or intervention not indicated
2	Moderate; minimal, local, or non-invasive intervention indicated; or limiting age-appropriate instrumental activities of daily living a
3	Severe or medically significant, but not immediately life-threatening; hospitalization or prolongation of hospitalization indicated; disabling; or limiting self-care activities of daily living b, c
4	Life-threatening consequences or urgent intervention indicated d
5	Death related to adverse event d

NCI CTCAE = National Cancer Institute Common Terminology Criteria for Adverse Events.

Note: Based on the most recent version of NCI CTCAE, v4.0, which can be found at: [http://ctep.cancer.gov/protocolDevelopment/electronic\\_applications/ctc.htm](http://ctep.cancer.gov/protocolDevelopment/electronic_applications/ctc.htm)

a Instrumental activities of daily living refer to preparing meals, shopping for groceries or clothes, using the telephone, managing money, etc.

b Examples of self-care activities of daily living include bathing, dressing and undressing, feeding oneself, using the toilet, and taking medications, as performed by patients who are not bedridden.

c If an event is assessed as a "significant medical event," it must be reported as a serious adverse event (see Section 5.4.2 for reporting instructions), per the definition of serious adverse event in Section 5.2.2.

d Grade 4 and 5 events must be reported as serious adverse events (see Section 5.4.2 for reporting instructions), per the definition of serious adverse event in Section 5.2.2.

### 5.3.4 Assessment of Causality of Adverse Events

Investigators should use their knowledge of the patient, the circumstances surrounding the event, and an evaluation of any potential alternative causes to determine whether an adverse event is considered to be related to any of the study treatment components,

indicating "yes" or "no" accordingly. The following guidance should be taken into consideration:

- Temporal relationship of event onset to the initiation of study treatment
- Course of the event, considering especially the effects of study treatment modifications or discontinuation of study treatment, or reintroduction of study treatment (as applicable)
- Known association of the event with the study treatment or with similar treatments
- Known association of the event with the disease under study
- Presence of risk factors in the patient or use of concomitant medications known to increase the occurrence of the event
- Presence of non-treatment-related factors that are known to be associated with the occurrence of the event

For patients receiving combination therapy, causality will be assessed individually for each protocol-mandated therapy.

